10.5.3 Sheath Removal

The sheath removal date and time will be determined by the treating investigator and the study subject's condition and coagulation status. The sheath(s) shall be removed as soon as possible after removal of the BEC. Before removal, the sheath should be carefully aspirated then flushed to eliminate any clots.

10.6 Tests Required 72 Hours (+12 hours) Following Start of r-tPA Administration

10.6.1 Assessments

1. **AE/SAEs** – Adverse events will be monitored and reported on the CRF post-procedure through discharge. *Bleeding complications will be assessed through 72 hours (-4 / +12 Hours) following initial administration of the first r-tPA dose that was administered in the IR suite/Cath lab.*

10.6.2 Data Collection

1. **Medications** – All medications will be recorded that are administered within 72 hours following the infusion.

10.7 Tests Required Just Prior to Hospital Discharge

10.7.1 Assessments

1. **Physical Examination** – The physician will perform a physical examination within eight (8) hours (-8 Hours) of discharge.
2. **AE/SAEs** – Adverse events will be monitored and reported on the CRF post-procedure through discharge.
3. **12-Lead Electrocardiogram** – To be done prior to and no greater than within eight (8) hours (-8 Hours) prior to discharge.

11.0 30-DAY FOLLOW-UP VISIT POST PROCEDURE

11.1 Assessments

1. **Physical Examination** – The physician will perform a physical exam at 30-day follow-up visit (± 7 days).
2. **AEs/ SAEs** – All adverse events will be recorded at the 30-day follow-up visit.

11.2 Data Collection

1. **Medications** – All medications since discharge will be recorded at 30-day follow-up.

12.0 ANTICIPATED ADVERSE EVENTS

The following events are anticipated adverse events in subjects who are treated for pulmonary embolism. An adverse event is any untoward medical occurrence associated with the use of a drug in humans, whether or not considered drug related (21 CFR 312.32(a)).

Suspected adverse reaction means any adverse event for which there is a reasonable possibility that the drug caused the adverse event. For the purposes of IND safety reporting, ‘reasonable possibility’ means there is evidence to suggest a causal relationship between the drug and the adverse event. A suspected adverse reaction implies a lesser degree of certainty about causality than adverse reaction, which means any adverse event caused by a drug. A suspected adverse reaction is an adverse event where there is a reasonable possibility the drug caused the adverse event. The sponsor is responsible for making the causality.

12.1 Bashir Endovascular Catheter Anticipated Adverse Events

Table 3. Anticipated Adverse Events Related to the Investigational Device¹⁸

Adverse Event	Definition
Allergic reactions	Any exaggerated immune response to a foreign antigen regardless of mechanism
Hematoma at access site	Blood collects under the skin in the area where the physician accessed the femoral artery to perform the treatment, and results in bruising (ecchymosis)
Hemorrhage	A profuse discharge of blood from a ruptured blood vessel resulting in a decrease in hemoglobin
Intimal damage	Trauma to the intimal lining of the vessel
Ischemia	Inadequate blood supply to an organ or part of the body or heart muscles
Pain and tenderness	Discomfort in an area that is impacted by the device
Vascular thrombosis	A formation of a blood clot in an artery or vein
Vessel perforation	A hole or tear in an artery or vein
Vessel spasm	A temporary tightening (constriction) of the muscles in the wall of one of the arteries that supplies blood flow

12.2 r-tPA Anticipated Adverse Events

Table 4. Anticipated Adverse Events Related to r-tPA Infusion¹⁵

Adverse Event	Definition
Fever	Elevated temperature above normal
Hematuria	Blood in the urine
Hematoma	Collection of blood under the skin
Hemoptysis	Coughing up blood
Hypotension	Sustained low blood pressure, below normal (Usually indicative of MAP< 60 mmHg)
Mucosal bleeding	Bleeding in the mouth
Pleural effusion	Fluid accumulation around the lung
Pulmonary edema	Fluid accumulation in the tissue and air spaces of the lungs
Pulmonary re-embolization	Sudden blockage of a major blood vessel
Thromboembolism	Obstruction of a blood vessel by a clot that has become dislodged

12.3 Anticipated Adverse Events Related to the Procedure

Table 5. Anticipated Adverse Events Related to the Procedure²⁰

Adverse Event	Definition

Access site pseudoaneurysm	Sometimes called a false aneurysm, occurs when a blood vessel wall is injured, and the blood is contained by the surrounding tissues
Anemia	Deficiency of red blood cells
Arrhythmia	Abnormal heart rhythm
Bleeding requiring blood transfusion	Any loss of blood that may or may not require medical intervention
Cardiac arrest	Permanent or temporary cessation of organized heart function requiring emergency CPR, cardioversion, or defibrillation
Death	The permanent end of vital processes in a cell or tissue
Ecchymosis	Bruising
Hematuria	Blood in the urine
Hemodynamic instability	Blood pressure requires vasopressor support.
Heparin induced thrombocytopenia	Caused by antibodies that bind to complexes of heparin and platelet factor 4 (PF4), activating the platelets and promoting a prothrombotic state
Infection	Bacteria in the blood or at the access site
Pain at access site	Discomfort at site of catheter insertion
Perforation	A hole or tear in a vessel
Pneumothorax	A presence of air or gas in the cavity between the lungs and the chest wall, causing collapse of the lung
Pulmonary infarct	Death of a portion of lung tissue caused by an interruption of blood supply
Shock	A life-threatening medical condition of low blood perfusion
Skin necrosis (if on warfarin)	A condition in which skin and subcutaneous tissues die due to long term treatment with warfarin

13.0 ADVERSE EVENT REPORTING

13.1 Serious Adverse Events and Serious Suspected Adverse Reactions

Serious adverse events (SAE) or serious suspected adverse reaction (SUSAR) must be reported to the study manager within 24 hours of knowledge of the event.

Serious adverse event or serious suspected adverse reaction: An adverse event or suspected adverse reaction is considered "serious" if, in the view of either the investigator or sponsor, it results in any of the following outcomes:

1. Death;
2. A life-threatening adverse event;
3. Inpatient hospitalization or prolongation of existing hospitalization;
4. A persistent or significant incapacity or substantial disruption of the ability to conduct normal life functions, or a congenital anomaly/birth defect;

5. Important medical events that may not result in death, be life-threatening, or require hospitalization may be considered serious when, based upon appropriate medical judgment, they may jeopardize the patient or subject and may require medical or surgical intervention to prevent one of the outcomes listed in this definition.

The following event definitions, as defined in 21 CFR 312.32(a) will be reported as serious adverse events and the reporting requirements above must be followed.

Life-threatening adverse event (or life-threatening suspected adverse reaction): An adverse event or suspected adverse reaction is considered "life-threatening" if, in the view of either the investigator or sponsor, its occurrence places the patient or subject at immediate risk of death. It does not include an adverse event or suspected adverse reaction that, had it occurred in a more severe form, might have caused death.

13.2 Unexpected Adverse Event or Unexpected Suspected Adverse Reaction

The following event definitions, as defined in 21 CFR 312.32(a) will be reported as serious adverse events and the reporting requirements above must be followed.

An Adverse Event or Suspected Adverse Reaction is considered "unexpected" if it is not listed in the investigator brochure or is not listed at the specificity or severity that has been observed; or, if an investigator brochure is not required or available, is not consistent with the risk information described in the general investigational plan or elsewhere in the current application, as amended.

It is anticipated that no unexpected adverse reactions will occur as r-tPA is FDA approved for the treatment of pulmonary embolism. The currently approved labeling requires 100mg of r-tPA to be administered intravenously over two (2) hours. This is 86mg more than the maximum dose required in this protocol administered over two (2) hours, not over approximately eight (8) hours as in this protocol.

13.3 Adverse Event Documentation

All adverse events (AEs) including those categorized as anticipated, life threatening, serious, unexpected, and suspected are to be reported on the case report form.

13.4 Adverse Event Relatedness

Table 6. Adverse Event Categories of Device Relatedness

Relatedness Term	Relatedness Definition
------------------	------------------------

Related	The adverse event is clearly related to the investigational agent/procedure – i.e. an event that follows a reasonable temporal sequence from administration of the study intervention, follows a known or expected response pattern to the suspected intervention, that is confirmed by improvement on stopping and reappearance of the event on repeated exposure and that could not be reasonably explained by the known characteristics of the subject's clinical state.
Possibly Related	An adverse event that follows a reasonable temporal sequence from administration of the study intervention follows a known or expected response pattern to the suspected intervention, but that could readily have been produced by a number of other factors.
Not Related	The adverse event is clearly not related to the investigational agent/procedure - i.e. another cause of the event is most plausible; and/or a clinically plausible temporal sequence is inconsistent with the onset of the event and the study intervention and/or a causal relationship is considered biologically implausible.

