 - v. Determine the total number of mls in the syringe and note 5ml is one-half of the volume of the solution for one-half of the dose.
 - vi. With a new syringe aspirate the amount of fluid from the IV bag that is equal in amount to one-half of the r-tPA solution in the r-tPA syringe, 5ml, so the total volume in the bag with the r-tPA will be 500cc once the 5mg of r-tPA is added to the IV bag. Repeat for second IV bag.
 - vii. Inject 5mg (5ml) solution of r-tPA into one (1) IV bag for infusion. Inject the second 5mg solution of r-tPA into the second IV bag for infusion. You should have a total of 5mg of r-tPA in a total of 500cc of diluent in each IV bag for bilateral PE, a total of 10mg split among the two IV bags.
 - viii. Set aside for use at the end of the pulse spray procedure(s).

3. Pulse Spray of r-tPA for Unilateral and Bilateral PE

- a. **Unilateral PE:** With the catheter in the target PA, and after verification the basket portion of the catheter has exited the sheath under fluoroscopy, and guidewire in place, expand the basket of the catheter to the desired diameter making sure that the infusion limbs are expanded to less than the diameter of the vessel wall.
- b. Attach the pulse spray syringe to the unused port of the stopcock attached to the basket infusion port. Pause the infusion pump of the r-tPA infusion. Turn the stopcock so that it is closed to the infusion pump line and open to the syringe and to the basket infusion port.
- c. Administer 10cc (1mg r-tPA in 10ml) of pulse spray, from the 1st syringe of two syringes, into the thrombus at a steady rate over 10-15 seconds.
- d. Under fluoroscopy, and guidewire in place, collapse the basket and re-expand the basket.
- e. Repeat this with the second 10cc syringe (1mg r-tPA in 10ml) over 10-15 seconds.

- f. As soon as the pulse sprays are administered, immediately re-start the r-tPA infusion via the basket infusion port of the BEC.
- g. **Bilateral PE:** Repeat steps a-f in contralateral pulmonary artery for bilateral PE.
- h. Once pulse sprays are complete, the basket(s) should remain expanded.
- i. As soon as the pulse sprays are administered, immediately re-start the r-tPA infusion via the basket infusion port of the BEC in accordance with Table 2. Refer to Section 9.3.2 and Table 2 for r-tPA infusion instructions.
- j. Remove the guidewire(s) from the wire lumen(s).

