10.2 Return to The IR suite/Cath lab at The Completion of Infusion

At the end of the infusion the patient returns to the IR suite/Cath lab within eight (8) hours (+8 hours) of the completion of the r-tPA infusion for removal of the BEC(s) and final hemodynamic measurements.

1. Under fluoroscopy, collapse the basket(s) of the BEC.
2. Remove the BEC by pulling the catheter(s) carefully into the sheath(s) and then removing them from the body.
3. Back bleed or aspirate the sheath(s) and flush with heparinized saline to prevent clot formation.
4. **Catheter for Hemodynamic Readings and Blood Draws:** Insert a Swan-Ganz or angled pigtail catheter through the sheath and record the following.
 - a. **Hemodynamic Readings**
 - i. SvO₂ – Mixed Venous Oxygen Saturations
 - ii. SpO₂ – Arterial Oxygen Saturation (pulse oximeter)
 - iii. PA Pressures: PAS / PAD / PA Mean

- iv. CO – Modified Fick calculation (Refer to Terms and Definitions for required calculation)
- v. CI – Calculation

b. Fibrinogen – To be drawn at the time of the device removal in the IR suite/Cath lab. *The assay method must be recorded (e.g. Clauss, PT-derived fibrinogen assay, immunological, gravimetric, other)*

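### Table 6 requires improvement on stopping and recurrence on re-exposure for Related, so a clear-cut device perforation or intimal injury fits none of its three grades

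*Combined protocol and SAP*

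**What the plan says.** Table 6 in section 13.4 is the only relatedness scale in the combined protocol and SAP. It has three grades and no unknown or default grade.

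- **Related** is introduced by *i.e.* and lists conditions joined together: reasonable timing, a known or expected response pattern, "that is confirmed by improvement on stopping and reappearance of the event on repeated exposure", and that the event "could not be reasonably explained by the known characteristics of the subject's clinical state".
- **Possibly Related** keeps the timing and pattern conditions and adds "but that could readily have been produced by a number of other factors".
- **Not Related** applies if "another cause of the event is most plausible", or if the timing does not fit, or if a causal link is biologically implausible.

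Table 3 in section 12.1 lists the adverse events anticipated from the device. They include vessel perforation ("A hole or tear in an artery or vein") and intimal damage ("Trauma to the intimal lining of the vessel").

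Each subject has one treatment course, and section 6.3.2, item 24 excludes re-enrolment. Some re-exposure occurs within that course. Section 9.3.1, item 3, step d reads "Under fluoroscopy, and guidewire in place, collapse the basket and re-expand the basket", and a second spray and a restart of the infusion follow. At catheter removal, section 10.2 reads "Insert a Swan-Ganz or angled pigtail catheter through the sheath and record the following".

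**The concern.** A relatedness scale should give every event a grade, above all the clearest cases. Here the top grade depends on a pattern of withdrawal and re-exposure. That suits a reversible reaction but not a structural injury. The events most plainly caused by the catheter are the ones that cannot meet it.

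This is a first-in-man study whose stated objective is the safety and feasibility of the device. A grader faced with a clear device injury must either ignore part of the definition or choose a lower grade, most likely Possibly Related. The second choice understates device causation, and two graders could resolve the same event differently.

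**Working it through.** The plan states no figure to reproduce. The check sets the three definitions side by side and tests cases against them.

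**Conditions taken from Table 6**

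- Related, all needed: R1 timing; R2 known pattern; R3 improvement on stopping; R4 reappearance on repeated exposure; R5 not explained by clinical state.
- Possibly Related, all needed: P1 timing; P2 known pattern; P3 other factors could readily have produced it.
- Not Related, any one suffices: N1 another cause most plausible; N2 timing inconsistent; N3 biologically implausible.

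**Cases**

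- A: perforation or intimal tear with plausible timing, known pattern and no other plausible cause.
- B: access-site hematoma that anticoagulation could readily explain, assuming anticoagulation is a ready cause but not the most plausible one.
- C: vessel spasm that resolves when the basket is collapsed and recurs when it is re-expanded, with no other cause.

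| Case | Related | Possibly Related | Not Related | Grades met as written | Grades met with *where applicable* |
|---|---|---|---|---|---|
| A | 3 of 5 (R3, R4 fail) | 2 of 3 (P3 fails) | 0 of 3 | 0 | 1 (Related) |
| B | not clearly related | 3 of 3 | 0 of 3 | 1 (Possibly Related) | 1 (Possibly Related) |
| C | 5 of 5 | 2 of 3 (P3 fails) | 0 of 3 | 1 (Related) | 1 (Related) |

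Counting R3 and R4 as one condition makes case A 3 of 4 on Related and changes nothing else. Case C shows that the condition can be met within one treatment course, so the gap does not rest on re-exposure being impossible. It rests on a tear not behaving in that way.

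**All combinations.** Treat R3 and R4 as one condition. The features are then timing, pattern, improvement with reappearance, not explained by clinical state, other ready factors, another cause most plausible, and biological implausibility. That gives 2^7 = 128 yes/no combinations.

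- As written, 11 combinations meet no grade.
- With *where applicable* waiving the improvement and reappearance condition, 10 meet no grade.
- The one removed (11 − 10 = 1) is case A.
- Of the remaining 10, eight have plausible timing but no known pattern. In the other two, the clinical state explains the event yet no other factor or cause is credited. These are separate from the point made here.

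**Size, if it were tabulated.** Section 16.2 promises descriptive statistics only and specifies no summary by relatedness. If one were produced, which is an assumption, one misgraded subject among the maximum of 10 would shift a per-subject proportion by 1/10 = 10 percentage points.

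**The case against.** The strongest reply is that little depends on the label. The endpoints in section 6.2, SAE reporting in section 13.5, the IND standard in section 12.0 and the stopping triggers in sections 18.2 to 18.4 do not use it. Under section 18.4.1, a suspected device-caused SAE goes to the independent data safety monitor, the device is returned and a root cause analysis follows. Under section 17.0 the monitor has the final say on every event. All of this stands and limits the harm. None of it supplies a grade in Table 6.

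A second reply is that *clearly related* governs and the rest only illustrates it. That would need *e.g.*; the text has *i.e.* and joins the conditions with *and*.

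A third is that Table 5 also lists perforation as a procedure event, and that other wires, sheaths and catheters enter the same vessels. Table 6 is titled for device relatedness but defines relatedness to agent or procedure. If the title governs, some perforations could be put down to those tools and fit Possibly Related. That is fair, and it narrows the gap to events with no ready alternative cause. It does not close it.

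Finally, *where applicable* calls for judgement. A transient event for which re-exposure was possible but did not happen could still be argued either way. The amendment also leaves untouched the title mismatch and the gap for events with plausible timing but no known pattern. Both limits are accepted.

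**Conclusion.** The concern holds. As written, Table 6 gives no valid grade (0 of 3) to a perforation or intimal injury with plausible timing, a known pattern and no other plausible cause. The improvement and reappearance clause is the sole reason. Events that anticoagulation or other factors could readily explain still fit Possibly Related.

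The consequence is limited to causality attribution of individual adverse events. No effect on an endpoint is claimed, and the 10-point figure is conditional on a tabulation the plan does not specify. The change should be made, but the study does not stand or fall on it.

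Confidence in the reading of Table 6 is high. What graders would do in practice is less certain, because the data safety charter (section 17.0) and the case report form (Appendix 21.4) were not available and could contain their own grading wording.

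**What to change.** In the Related row of Table 6, insert the words *where applicable*, set off by commas, after *confirmed* in the clause on improvement and reappearance. Leave the rest of that row and the other two definitions as they are. If the data safety charter has its own relatedness wording, make it match.

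Check the amended table with two cases. A perforation with no other cause must fall only in Related. An access-site hematoma readily explained by anticoagulation must stay only in Possibly Related.

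The cost is two words in one table, with no new data and no new case report form fields. The downside is that slightly more events will be labelled related.

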13.5 Investigator SAE Reporting Requirements

An SAE occurring during the study or within 30 days of stopping the treatment must be reported to the study safety monitor. Any such SAE due to any cause, whether or not related to the study medication, must be reported within 24 hours of occurrence or when the investigator becomes aware of the event.

The investigator must send a preliminary report of any such SAE to the project manager via the EDC system within 24 hours or if this is not possible via email or fax using an SAE Report Form, or at a minimum by telephone.

The event must be recorded on the electronic SAE CRF page. Preliminary reports of SAEs must be followed by detailed descriptions, including clear pseudonymized photocopies of hospital case reports, consultant reports, autopsy reports, and other documents when requested and applicable. All photocopies should be redacted to remove patients' personal details and annotated with the patient's unique study identifiers. SAE reports must be made whether or not the investigator considers the event to be related to the investigational drug. Appropriate remedial measures should be taken to treat the SAE, and the response to treatment should be recorded. Patients must be closely followed until sufficient information is obtained to indicate a return to normal status or until the event stabilizes at a level acceptable to the investigator.

14.0 REGULATORY REQUIREMENTS

The following are requirements of the sponsor and of the investigators.

14.1 Investigator Responsibilities

The following responsibilities are required for investigators participating in this study:

An investigator is responsible for ensuring that the investigation is conducted according to the signed agreement, the protocol, and applicable FDA regulations, for protecting the rights, safety and welfare of subjects under the investigator's care and for the control of devices under investigation. An investigator also is responsible for ensuring that informed consent is obtained in accordance with CFR part 50. [21 CFR 312 Subpart D]. Specific responsibilities include:

1. An investigator is responsible for ensuring that an investigation is conducted according to the signed agreement, the protocol and applicable FDA regulations, for protecting the rights, safety, and welfare of subjects under the investigator's care, and for the control of devices under investigation. An investigator also is responsible for ensuring that informed consent is obtained in accordance with part 50 of this chapter. Additional responsibilities of investigators are described in subpart G.
2. Awaiting approval: an investigator may determine whether potential subjects would be interested in participating in an investigation but shall not request the written informed consent of any subject to participate and shall not allow any subject to participate before obtaining FDA and IRB approval.
3. Compliance: an investigator shall conduct an investigation in accordance with the signed agreement with the sponsor, the investigational plan, any applicable FDA regulations and any conditions of approval impose by an IRB or FDA.
4. Supervising Device and Drug Use: an investigator shall permit an investigational device and drug to be used only with subjects under the investigator's supervision and shall not supply an investigational device to any person not authorized under FDA regulation to receive it. The r-tPA, sterile water, and 0.9% NaCl for infusion will be provided by the site. Detailed documentation of the dosage and administration of the drug will be performed by the site for each study subject. Disposition of each study device will be documented by the site.
5. Financial Disclosure: an investigator shall disclose to the sponsor sufficient accurate financial information to allow the applicant to comply with 21 CFR 54 and shall promptly update this information if any relevant changes occur during the course of the investigation and for 1 year following completion of the study.
6. Form 1572 will be completed and signed by the investigator prior to commencement of the study.
7. Disposing of Device and Drug: upon completion or termination of the investigator's part of an investigation, return to the sponsor any remaining supply of the device or otherwise dispose of the device as the sponsor directs.
8. Investigator Records and Reports: participating investigator shall maintain the following accurate, complete, and current records relating to the investigator's participation in an investigation:
 - a. All correspondence with another investigator, an IRB, the sponsor, a monitor, or FDA, including required reports.
 - b. Records of receipt, use or disposition of a device that relate to:

- i. The type and quantity of the device, the dates of its receipt, and the batch number or code mark.
 - ii. The names of all persons who received, used, or disposed of each device.
 - iii. Why and how many units of the device have been returned to the sponsor, repaired, or otherwise disposed of.
9. Records of each subject's case history and exposure to the device. Case histories include the case report forms and supporting data including, for example, signed and dated consent forms and medical records including, for example, progress notes of the physician, the individual's hospital chart(s), and the nurses' notes. Such records shall include:
 - a. Documents showing evidence of informed consent and, for any use of a device by the investigator without informed consent, any written concurrence of a licensed physician and a brief description of the circumstances justifying the failure to obtain informed consent. The case history for each individual shall document that informed consent was obtained prior to participation in the study.
 - b. All relevant observations, including records concerning adverse device effects (whether anticipated or unanticipated), information and data on the condition of each subject upon entering, and during the course of, the investigation, including information about relevant previous medical history and the results of all diagnostic tests.
 - c. A record of the exposure of each subject to the investigational device, including the date and time of each use, and any other therapy.
10. The protocol, with documents showing the dates of and reasons for each deviation from the protocol.
11. Any other records that FDA requires to be maintained by regulation or by specific requirement for a category of investigations or a particular investigation.
12. The Principal Investigator is required to prepare and submit to the Sponsor the following complete, accurate, and timely reports on this investigation, when necessary:
 - a. Withdrawal of IRB approval (within 5 working days)
 - b. Progress report, if applicable (annually)
 - c. Deviations from the protocol (Not permitted unless to protect the health, safety, welfare of the patient)
 - d. Informed consent deviations (within 5 working days)
 - e. Final report
13. Core Lab Data Acquisition: Provide core labs with recorded media according to the core lab protocols within the specified timeframe in the core lab instruction manual. Independent core lab for CTA and Echocardiograms:

Medical Metrics, Inc.
[name]
14. Publication: The Principal Investigator shall not create any publication related to this study without the express written permission of the sponsor. Should the principal investigator wish to publish or present the results of single-center results

from this study, the principal investigator agrees to collaborate with the principal investigators participating in this study and provide the sponsor with an abstract, manuscript, and/or presentation for review 60 days prior to submission for publication or presentation. Once initial results are published, the site principal investigator may publish single-center results in collaboration with the sponsor.

The sponsor retains the right to delete from the manuscript confidential information and to object to suggested publication and/or its timing (at the device manufacturer's sole discretion).

